6. STUDY DESIGN

This is a prospective, randomized, controlled study of children with persistent asthma who are managed on daily inhaled corticosteroids (ICS). 75 children will be randomized **2:1** into one of two arms:

- 50 children will be randomized to BreatheSmart, comprised of:
 - BreatheSmart mobile application that tracks medication usage and sends real time reminders
 - HeroTracker sensor that counts dosage and monitors real-time medication adherence
 - CoheroConnect provider portal that allows the Investigator to monitor real-time adherence and to provide targeted outreach to children with low adherence (intervention arm)
- 25 children will be randomized to “standard of care” (control arm). These patients are reminded to adhere to the prescribed standard of care therapy provided by their clinician during their clinical encounters and when the family calls to report an illness.

6.1.Endpoints

6.1.1 Primary:

The study's primary objective is to estimate the relative improvement in medication adherence among children using BreatheSmart with feedback compared to control at 6 months.

6.1.2 Secondary:

Important secondary objectives include the extent to which BreatheSmart system improves the following when compared to control from baseline to 6-months:

- asthma control as measured by the Childhood Asthma Control Test (ACT)
- lung function as measured by FEV1 and FEV1/FVC ratio compared to standard of care
- the correlation between changes in medication adherence and changes in FEV1 and FEV1/FVC ratio.
- the overall number of provider visits for asthma related adverse events (number of exacerbations leading to acute Provider intervention, ER visits, hospitalizations, or requiring oral systemic corticosteroid therapy)
- number of missed school days

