8.4. Follow-up

All participants in both groups will be seen at 90 and 180 days' post randomization (+/-20 days) correlating with routine pulmonary clinic follow up and East and West Primary Care Follow up where the following assessments will be recorded:

- Medication changes/refills (obtained through pharmacy record)

- FEV1, FEV1/FVC, FEF25-75 and FeNO per clinical standard of care (only assessed in the Pulmonary clinic)
- Child Asthma control test (ACT) questionnaire
- Serious Adverse Events will be recorded at each visit
- Missed school days
- PedsQL asthma module (patient and parent report)
- Test of Adherence to Inhalers
- Exacerbation of asthma episodes (obtained through self-report and chart review) requiring:
 - Doctor visits outside of standard of care
 - ER visits
 - Hospitalizations

In addition, active participants (test group) will be continuously monitored via the CoheroConnect dashboard which allows the Investigator to monitor the child's medication adherence in real time. If a period of participant inactivity of 3 days is registered in the system, the Investigator (or designee) will be notified and he/she will be prompted to contact the participant to remind them to take their medication as prescribed. The Investigator or designee will review patient specific data (% adherence since last visit and graph of adherence patterns over time since enrollment) through the CoheroConnect dashboard within two days before a follow up visit. At the follow-up visit, these data will be reviewed with the patient and parent/caregiver. The adherence rate and barriers identified will be discussed and, if necessary, personalized strategies for improvement will be devised. These data will also be shared with the clinician during these follow up visits. Medication adherence data for control participants will be obtained by measure of pharmacy record refill information and self-report (Test of Adherence to Inhalers) throughout the duration of the study.

We understand that the self-report of missed school days due to asthma may be unreliable and subject to recall bias, however, this is the method we currently use clinically to assess this measure.

If a participant is unable to complete the follow-up visit at their routine pulmonary appointment, the coordinator will either mail, text a link, or email a link of the follow-up surveys to the participants. They will be reminded 3 times via text, email or phone to complete the follow-up questionnaires.

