10.5. Statistical Analysis

Between group differences in the change in mean adherence from baseline over will be based on a 0.05 level t-test. The corresponding 95% confidence interval for the between group mean difference will provide an interval estimate of benefit obtained using the Cohero system. [NR1]

In addition to the frequentist analysis of adherence, a Bayesian approach that focuses on estimating the probability distribution of differences in mean adherence using the Cohero system compared to standard of care. The Bayesian approach begins with the premise that the Cohero system yields no improvement in adherence. This is an exact correspondence to a “null hypothesis”. This assumption is incorporated through a prior distribution for improvement in mean adherence; for example, by assuming that the mean improvement is characterized by a normal distribution with mean 0, the expected difference should the Cohero system offer no benefit, and some small variance (e.g. 0.01). This is also a statement that the probability that the Cohero system improves response compared to standard of care is 50% (i.e., the prior odds that active therapy is effective is 1:1, consistent with the notion of equipoise).

The essence of the Bayesian approach is to use the data collected during the study to update the prior probability density based on the observed data (this updated density is the posterior probability distribution) using Bayes Theorem. This posterior distribution provides estimates of the probability that the Cohero system improves adherence relative to standard of care by any amount greater than δ . For example, choosing $\delta=0$ corresponds to the frequentist test of the null hypothesis.

The analysis of lung function will be performed in a corresponding manner to that described for adherence. Additionally, the correlation between change in FEV1, FEV1/FVC ratio and FEF25-75 and change in adherence will be computed. Graphical analysis will be used to visually inspect the relationship between improvement in adherence and improvement in lung function. Based on the general form of the relationship, additional exploratory analyses will be performed. For example, if the relationship is approximately linear, standard regression methods will be used to estimate the relationship; if, however, a clear discontinuity is seen, splines might be used to estimate the relationship.

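### Sections 10.4–10.5 make no use of the day-90 values and give no missing-data rule; for lung function, the t-test on change would leave out a child who has no day-180 spirometry

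*Combined protocol and SAP*

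**What the plan says.** On visits, section 8.4 states: "All participants in both groups will be seen at 90 and 180 days". Each visit records ACT, PedsQL, the Test of Adherence to Inhalers, missed school days and exacerbations. Lung function is listed as "FEV1, FEV1/FVC, FEF25-75 and FeNO per clinical standard of care (only assessed in the Pulmonary clinic".

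On timing, section 6.1.2 asks how far the system "improves the following when compared to control from baseline to 6-months", and 6.1.1 sets the primary objective at the same time point.

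On analysis, section 10.5 says: "Between group differences in the change in mean adherence from baseline over will be based on a 0.05 level t-test". The period after the word over is missing, so 6 months has to be inferred from section 6.1. A 95% confidence interval and a Bayesian analysis of the mean difference follow, and then the sentence on lung function: "The analysis of lung function will be performed in a corresponding manner to that described for adherence". No test is stated for ACT.

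Section 10.4 makes primary and secondary analyses intention-to-treat and defers detail to a SAP still to be developed. Apart from the visit schedule, the 90-day visit appears only in 10.3, for data-entry spot checks.

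**The concern.** A change score needs both ends. With no imputation rule and no model for intermediate visits, a child without a day-180 measurement cannot enter a t-test on 6-month change, even if the day-90 result is on file. The analysis set then becomes those measured at day 180 rather than those randomised.

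Two things are at stake. The first is precision, in a trial with only 25 controls. The second is bias if loss is selective and differs by arm. That is plausible here: the trial is open, visits follow routine clinic appointments, non-responders may be withdrawn after three attempts (8.6), and only the active arm is monitored continuously and contacted after 3 days of inactivity (8.4).

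**Working it through.** The plan states no SD, effect size, dropout rate or correlation, so there is no figure to reproduce. The only inputs from the documents are 50 and 25 children (section 6) and the 0.05 level and 95% interval (10.5). Everything else below is assumed.

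**1. Which outcomes are exposed**

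| Outcome | Source if the day-180 visit is missed | Test in 10.5 |
|---|---|---|
| Adherence | Refill records (control); sensor data (active) | t-test on change |
| FEV1, FEV1/FVC | None; Pulmonary clinic only | As for adherence |
| ACT | Surveys by mail, text or email, with three reminders (8.4) | None stated |
| PedsQL | As for ACT | None stated; not a listed objective |

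Only lung function has both a stated t-test and no route to a day-180 value without the visit.

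**2. Precision**

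The half-width of the 95% interval is t × SD × √(1/n₁ + 1/n₂).
- All 75 children: 1.993 × √(1/50 + 1/25) = 0.488 SD.
- 20% missing (40 and 20): 2.002 × √(1/40 + 1/20) = 0.548 SD.

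These are best cases for lung function. Children seen in primary care have no spirometry, and the split between clinics is not given.

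Let ρ be the correlation between change to day 90 and change to day 180. With n_c children measured at day 180 and n_s measured at day 90, the likelihood estimate has variance proportional to (1 − ρ²)/n_c + ρ²/n_s, against 1/n_c for complete cases. For ρ = 0.5, n_c = 60 and n_s = 75, this is 0.75/60 + 0.25/75 = 0.01583, an effective N of 63.2. The SE ratio is √(60/63.2) = 0.975.

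| ρ | Effective N (SE ratio), all dropouts seen at day 90 | Half of them seen |
|---|---|---|
| 0.3 | 61.1 (0.991) | 60.6 (0.995) |
| 0.5 | 63.2 (0.975) | 61.7 (0.986) |
| 0.7 | 66.5 (0.950) | 63.5 (0.972) |

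If all dropouts were seen at day 90, the SE falls by 0.5–2.5% at 10% missing and by 1.4–7.6% at 30% missing.

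Simulations used 50:25 and correlations of 0.4–0.6 (baseline to day 180) and 0.6–0.7 (day 90 to day 180). Adding day 90 gave about 2–8% more information than a baseline-adjusted complete-case analysis; one wider set of correlations reached 10%. The separate gain from baseline adjustment is not counted.

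**3. Bias in the raw-change test**

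Write r(a,b) for the correlation between visits, with unit variances. Selective loss matters only so far as its driver is correlated with the 6-month change.
- Driver is the day-90 level: covariance = r(90,180) − r(0,90). With 0.65 and 0.60 this is 0.05.
- Driver is change by day 90: covariance = r(90,180) − r(0,90) − r(0,180) + 1. With r(0,180) = 0.50 this is 0.65 − 0.60 − 0.50 + 1 = 0.55. Per SD of the driver, 0.55/√(2 × 0.40) = 0.61.

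In the simulations, raw-change bias was therefore about 0–0.02 SD when loss depended on the day-90 level. It reached at most 0.05 SD when the baseline-to-day-90 correlation was allowed to be as low as 0.3. It was about 0.03–0.09 SD when loss depended on change by day 90. A direct calculation agrees: with 20% loss in one arm and an odds ratio of 2 per SD lower change by day 90, that arm's mean shifts by 0.040, 0.062 and 0.089 SD for ρ = 0.3, 0.5 and 0.7. With day 90 in the model, bias was near zero in both cases, because these settings are missing at random given baseline and day 90.

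**4. A case where the model does worse**

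If loss depends on a child's stable underlying level, more strongly in one arm, subtracting baseline removes that level. Raw change is then unbiased (within 0.01 SD), while the model carries about 0.02–0.06 SD.

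**The case against.** The trial is exploratory, its size is set by device supply (7.2), and 10.4 promises a fuller SAP. The plan is silent on missing values; it does not say that children are dropped. The information gain is small, and where loss depends on the day-90 level the bias is negligible beside a half-width of about 0.55 SD.

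All of that stands and limits the weight of the point. It does not remove the gap: the method that is written down cannot use a child without a day-180 FEV1, and nothing in 10.4 or 10.5 says how such a child is kept under intention-to-treat.

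Three stronger readings are tempting and are not supported:
- A reader might infer that any child who misses day 180 is lost from every outcome. Refill and sensor data do not need the visit, surveys can be completed remotely, and day-90 reports of exacerbations and missed school days would presumably feed the 6-month totals.
- A reader might attach to this plan the bias of 0.04–0.09 SD found for a baseline-adjusted complete-case analysis when loss depends on the day-90 level. The plan does not name that analysis.
- A reader might infer that the model needs strictly weaker assumptions than the t-test. Raw change needs loss unrelated to change; the model needs loss at random given what was observed. Neither implies the other, as step 4 shows.

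**Conclusion.** The point holds in a limited form. It bears fully on lung function, on ACT only when the remote surveys go unanswered, and not on adherence. The exclusion is inferred from the change-score test, from the 6-month time point in section 6.1, and from the absence of a missing-data rule.

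The plausible bias of 0–0.09 SD is at most about 16% of the 95% half-width (0.09/0.548). All sizes rest on assumed dropout of about 20%, assumed correlations and an assumed dropout mechanism. The stronger reason to act is that the intention-to-treat statement has no working meaning for lung function as the plan is written.

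**What to change.** In the SAP:
1. Complete the sentence in 10.5 by naming the period (baseline to 6 months, if that is what is meant).
2. For FEV1, FEV1/FVC and ACT, specify a likelihood-based repeated-measures model on baseline, day 90 and day 180. It should have a mean at baseline common to both arms, visit, arm-by-visit and age stratum, with unstructured covariance and REML with small-sample degrees of freedom. The day-180 contrast is the stated effect; day 90 is descriptive. For ACT this supplies a comparison that 10.5 lacks.
3. Report the raw-change complete-case t-test as a sensitivity analysis, since it is robust to loss tied to a child's stable level and the model is not.
4. State the missing-at-random assumption, and report by arm how many children have day-90 but no day-180 values.

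The cost is SAP wording and standard software. The model also estimates the within-child correlations, which serves the aim in 10.4 of informing a larger study.

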11. STUDY CONDUCT

11.1. Good Clinical Practice

The study will be conducted in accordance with the International Conference on Harmonization (ICH) for Good Clinical Practice (GCP) and the appropriate regulatory requirement(s). The investigator will be familiar with evidenced-based standard of care practice in the treatment of patients with asthma, the prescribing information of medications, and with the risks and potential benefits of the study. Essential clinical documents will be maintained to demonstrate the validity of the study and the integrity of the data collected. Master site files will be established at the beginning of the study, maintained for the duration of the study, and retained according to the appropriate regulations.

11.2. Ethical Considerations

The study will be conducted in accordance with ethical principles founded in the Declaration of Helsinki. The Institutional Review Board (IRB)/Independent Ethics Committee (IEC) at each participating institution will review all appropriate study documentation in order to safeguard the rights, safety, and well-being of the participants. The study will only be conducted at sites where IRB approval has been obtained. The protocol, informed consent, recruitment advertisements (if applicable), written information given to the participants (including user manuals), safety updates, annual progress reports, and any revisions to these documents will be provided to the IRB by the investigator or study sponsor.

11.3. Institutional Review

Prior to initiation this study must be approved by the CT Children's institutional review board (IRB) committee as defined by Federal Regulatory Guidelines (Ref. Federal Register Vol. 46, 17, January 27, 1981, part 56) and the Office for Protection from Research Risks Reports: Protection of Human Subjects (Code of Federal Regulations 45 CFR 46).

11.4. Participant Information and Informed Consent

The principles of informed consent are described by Federal Regulatory Guidelines (Federal Register Vol. 46, No. 17, January 27, 1981, part 50) and the Office for Protection from Research Risk Reports: Protection of Human Subjects (Code of Federal Regulations 45 CFR Part 46). They must be followed to comply with IRB regulations for the conduct and monitoring of clinical investigations. Freely given written informed consent must be obtained from every participant prior to clinical study participation.

11.5. Participant Confidentiality

In order to maintain participant privacy, all CRFs, study reports, and communications will identify the participant by the assigned alpha-numeric study number. Only study personnel will have access to the participant's original medical records for verification of data gathered on the CRFs and to audit the data collection process. The participant's confidentiality will be

maintained and will not be made publicly available to the extent permitted by the applicable laws and regulations.

11.6. Protocol Compliance

The investigator will conduct the study in compliance with this protocol and supporting documents. Any changes to the protocol will require approval from the IRB prior to implementation, except when the modification is needed to eliminate an immediate hazard(s) to participants. Any departures from the protocol must be fully documented in the source documents and the EDC.

11.7. On-site Audits

The IRB may request access to all source documents, data capture records, and other study documentation for on-site audit or inspection. Direct access to these documents must be guaranteed by the investigator, who must provide support at all times for these activities.

11.8. Record Keeping and Retention

Data generated for the study will be stored in a limited-access file area and be accessible only to study personnel. All reports and communications relating to study participants will identify participants only by participant identification code. Complete participant identification will be kept by the investigator. This information will be treated with strict adherence to professional standards of confidentiality. An investigator must in reasonable time, upon request from any properly authorized officer or employee of FDA/relevant health authority or regulatory agency, permit such officer or employee to have access to requested records and reports, and copy and verify any records or reports made by the investigator. The investigator will also grant the representatives the same privileges offered to FDA/relevant health authority or regulatory agents/officers/employees.

11.9. Site Master File

The following documents will be retained in the site master file:

- Current signed curriculum vitae and medical licenses (within 1 year) for the Principal Investigator and all co-investigators.
- A copy of the IRB approval letter. Renewals must be submitted at annual intervals or as required by IRB policy.
- A copy of the IRB approved informed consent form
- IRB member list and DHHS General Assurance Number (FWA number).
- A fully executed clinical study agreement
- Signed Financial Disclosure Form
- The Investigator Protocol Agreement Form signed and dated by the Principal Investigator at each site.

In addition to the documents listed above, the PI will also retain the following items:

- All original informed consent forms with required signatures
- All IRB correspondence (i.e., informed consent [including any approved revisions], protocol, advertisements, newsletters)
- Training Logs
- Copies of all correspondence pertaining to the study between the Sponsor, Site and the Participants
- Study Monitoring Log
- Delegation of Authority Log
- Device Accountability Log

All study-related records must be maintained in accordance with local IRB policies. The investigator will not discard any records until completion of the study.

Asthavent 100 mcg	Foster 100/6 mcg
Atimos 12 mcg (50 count), (100 count) and (120 count)	Ipvent HFA 40 mcg
Beclate HFA 50 mcg, 100 mcg, 200 mcg	QVAR 40 mcg, 80 mcg
Budeflam 100 mcg	Serevent Diskus
Ciclovent 160 mcg	Seroflo 50 mcg, 125 mcg, 250 mcg
Clenil 50 mcg, 100 mcg, 200 mcg, 250 mcg	Symbicort 80/4.5 mcg, 160/4.5 mcg, 400/12 mcg
Rescue	
Atrovent HFA	
ProAir HFA	
Proventil HFA	
Ventolin HFA 60 count, 200 count	
Xopenex HFA 80 count, 200 count
